1.4.2.4 Entolimod in Combination with Vaccine

The Kadvax Technology study was performed to evaluate the safety and efficacy of 1 µg of entolimod receiving a commercial tetanus-diphtheria (Td) vaccine in healthy human subjects. The study enrolled 40 male volunteers (16 Caucasian, 24 non-Caucasian) between the ages of 18 and 40 years old (mean age = 28 years). Fifteen volunteers were enrolled in the control group and given commercial Td vaccine alone while 25 volunteers received the Td vaccine in combination with 1 µg of entolimod. Tetanus- and diphtheria-specific antibody titers were to determine if the addition of entolimod increased the vaccine response.

Mean baseline levels of tetanus toxoid (TT) -specific antibodies were relatively high in this study (2.95 IU/mL), and as a result, no subjects in the control (Td alone) or test (Td+entolimod) group had TT antibody responses above 6 IU/mL. Therefore, only subjects with pre-treatment-antibody titers below 3 IU/mL were included for data analysis (9 Td alone and 11 Td+entolimod). Eighty-two percent of the subjects that received entolimod with the Td vaccine showed a 2-fold or higher increase in their TT antibody titers, while only 33% of the control group showed this level of increase (chi sq = 4.3; p = <0.03). Two of the entolimod test subjects showed particularly strong increases in antibody titers (10- and 15-fold above baseline). A negative correlation was observed between baseline antibody titer and the change in antibody titer over 6 weeks. The correlation between lower baseline titer and greater post-vaccination change in titer was stronger in the Td+entolimod group than in the control group ($r = -0.73$ vs. -0.36). The negative correlation was statistically significant in the Td+entolimod test group with a p-value of <0.003. Analysis of anti-diphtheria antibody titers showed a greater increase in anti-diphtheria antibody titers for all 25 Td+entolimod test subjects versus the 15 Td alone control subjects (averaging 1.1 IU/mL vs. 0.9 IU/mL, respectively; p = <0.02). The negative correlation between baseline antibody titer and the change in anti-diphtheria antibody titer was also significantly stronger for the Td+entolimod group than for the control group ($r = -0.91$ vs -0.52 , respectively).

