- Blood work for pharmacodynamics, vaccine related antibodies, LINE-1, serum antibody testing, and peripheral blood mononuclear cells (PBMCs) prior to vaccine and investigational product administration and 2, 4 and 6 hours post administration
- SAVE procedures (if applicable)

After the observation period (6 hours) and prior to discharge from the Clinical Research and Trials Unit, a reassessment of vital signs including orthostatic blood pressures will be conducted on all study participants.

6.3 Visit 3, Safety Follow-up –Day 1

This visit will be recorded as “Day 1” and will require a visit to the research center where the following tests will be performed:

- Brief physical examination
- Vital signs (orthostatic blood pressure, oxygen saturation, temperature, respiratory rate, weight, and heart rate)
- Review of medications
- Review of adverse events
- Respiratory infection assessment
- Quality of Life (QoL) questionnaire
- ECG
- Blood work – labs [serum chemistry, Hematology, coagulation, cytokines, LINE-1, and vaccine related antibodies]
- Urine collection for urinalysis

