6.15 Adverse Events

Adverse event monitoring will be conducted throughout the study for all subjects. The AE and serious adverse event (SAE) reporting period begins at the time of informed consent and continues through study completion. Adverse events will be assessed at every site and remote visit.

The Investigator will follow-up on all AEs observed or reported by the subject up to the end of the reporting period or until follow-up is no longer necessary. The Investigator will follow-up on SAEs until they are considered resolved or the outcome is known.

Definitions, documentation, and reporting of AEs are described in Section 8. Serious adverse events must be reported within 24 hours as described in Section 8.2.

Table S-1. Schedule of Events

PERIOD	Screening Visit	Treatment Visit	Safety Follow-Up		Monthly Follow-Up					
ON-SITE VISIT	1	2	3	4 (remote)	5	6	-	7	-	8
WEEK	-4	0	Day 1	1						
MONTH					1	2	3 to 5 ^[p]	6	7 to 11 ^[p]	12
Visit Window, week(s)	-28 days			± 1 day	± 1 week					
General Eligibility, Safety, and Frailty Assessments										
Eligibility assessment	X									
Written informed consent	X									
MMSE cognitive status assessment	X									
Frailty assessments ^[a]	X						X	X		X
Brief physical examination ^[b]	X		X							
Medical history	X									
Demographic Information	X									
Vital signs/oxygen saturation/Ht/Wt ^[c]	X ^[q]	X ^{[d][q]}	X ^[q]		X ^[q]	X ^[q]		X ^[q]		X ^[q]
12-lead ECG	X		X		X	X		X		X
AE assessment, including respiratory infection assessment	X	X	X	X	X	X	X	X	X	X
Concomitant medications	X	X	X	X	X	X	X	X	X	X
Quality of life (QoL) questionnaire	X		X	X	X	X	X	X	X	X
Study Drug Administration										
Study drug		X								
Laboratory Assessments										
Serum chemistry ^[e]	X		X		X	X		X		X
Hematology ^[f]	X		X		X	X		X		X
Coagulation ^[g]	X		X		X	X		X		X
Serum virology ^[h]	X									
Urinalysis ^[i]	X		X		X	X		X		X
Serum for entolimod-reactive antibodies ^[j]	X		X		X	X		X		X
Plasma for pharmacodynamics ^[k]		X								
Serum for vaccine related antibodies ^[l]		X			X	X		X		X
Peripheral blood mononuclear cells (PBMC) ^[m]		X			X	X				X
COVID-19, PCR [SARS Coronavirus 2, Molecular Detection, PCR (NP)]		X								X
Exploratory Procedures										
SAVE ^[n]		X								
Biomarkers of senescence ^[o]		X			X			X		X
SARS-CoV-2 IgG Ab [SARS Coronavirus 2 IgG Ab, Serum]		X								X

Footnotes
[a] To be collected at screening, baseline, months 2, 6 and 12 (includes questionnaires, physical function testing, and body composition)

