7.1 Sample Size Determination

A sample size of 25 per arm provides 90% power to detect a doubling (100% increase) in geometric mean influenza antibody titer A/H1N1 based on a one-sided two-sample t-test at alpha level 0.15. This calculation assumes a coefficient of variation of 2.0 for A/H1N1. Under the assumption of smaller coefficient of variation for A/H3N2 and B antibody titers of 1.4, 25 per arm provides 90% power to detect an 80% increase in these antibody titers at alpha level 0.15. Thus, we plan to enroll 25 to each arm, for a total sample size of 100. We anticipate greater power under the ANCOVA approach, adjusted for baseline levels of the titer.

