The distribution of antibody titers (A/H1N1, A/H3N2, B) during follow up is anticipated to be skewed based on reporting in prior studies and a log-transformation will be applied to these outcomes. Antibody titers are measured at multiple time points in the first week after treatment, 4 weeks, 2 months, 6 months, and 12 months. A hierarchical mixed-effects regression model will be fit separately for the 3 endpoints, adjusting for the baseline/screening observation of the titer (an analysis of covariance (ANCOVA) approach). The model will include random subject-specific intercepts and model time as discrete. The primary outcome comparison is a contrast analysis of the outcome at 4 weeks comparing each entolimod dose to placebo. As the overall aim of this study is to assess safety and identify potential efficacy of entolimod, especially the dose most likely to succeed in Phase III study, we apply a one-sided test at alpha level 0.15 to each dose comparison (vs. placebo) and antibody titer combination, without multiplicity adjustment. The primary analysis will be conducted using the modified intent-to-treat analysis dataset.

Secondary Hypotheses: Secondary and exploratory endpoints require a variety of standard statistical methods.

Key secondary endpoints include the frailty indices, measures of physical function (6 minute walk test and grip strength), and quality of life (QOL). Frailty indices are measured at 2, 6, and 12 months and QOL measured at each study visit. For these outcomes, linear mixed effects models will assess the relationship between randomized arm and outcomes over time. Discrete times will be considered corresponding to the study visit and secondary analyses may consider continuous linear time (constant slope over time) for changes in the outcome. For these outcomes, the 12 month observation is the primary comparison.

Upper respiratory infections, including influenza, will be recorded over the follow up period. We anticipate the total number of these will be infrequent. Thus, we compare the outcome of any infection (vs. no infection) across randomized arms using a Pearson chi-square test or Fisher's exact test. Secondary approaches may consider analysis of the ordinal count of the number of infections, analyzed using a trend test.

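### Section 7.2 models first-week titers that Table S-1 does not schedule; if those drawn within 24 hours of dosing enter the primary model, the week-4 test exceeds its 0.15 error level and loses a little precision

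*Combined protocol and SAP*

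**What the plan says.** - **Section 7.2, titer times:** "Antibody titers are measured at multiple time points in the first week after treatment, 4 weeks, 2 months, 6 months, and 12 months".
- **Section 7.2, model:** log titers in a mixed model with random subject intercepts, discrete time and adjustment for the baseline or screening titer. No baseline-by-visit term and no visit-specific variance is mentioned; neither is ruled out. The primary comparison is each dose against placebo at 4 weeks.
- **Section 7.2, test:** "we apply a one-sided test at alpha level 0.15 to each dose comparison (vs. placebo) and antibody titer combination".
- **Section 6.2 (Day 0):** vaccine-related antibodies are in a blood-work list that ends with "peripheral blood mononuclear cells (PBMCs) prior to vaccine and investigational product administration and 2, 4 and 6 hours post administration".
- **Section 6.3 (Day 1):** vaccine-related antibodies are listed again. The Day 7 visit (6.4) is remote and has no blood draw.
- **Table S-1:** the row "Serum for vaccine related antibodies" is marked at the Treatment Visit and Months 1, 2, 6 and 12 only. The footnote with the 2, 4 and 6 hour draws belongs to the plasma G-CSF and IL-6 row; the titer footnote gives no times.
- **Section 7.1:** "We anticipate greater power under the ANCOVA approach, adjusted for baseline levels of the titer".

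**The concern.** Taken together, 7.2, 6.2 and 6.3 supply up to four post-dose titers (2, 4, 6 and about 24 hours) as outcomes. A vaccine response is not expected that soon, so these values should be close to a second reading of baseline: regression slope on baseline near 1, little residual scatter. At 4 weeks the slope should be lower and the scatter much larger.

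A model with one baseline slope and one common variance then goes wrong in two ways. The slope used at week 4 is too steep, which costs precision. The variance used at week 4 is averaged over quiet and noisy visits, which makes the standard error too small. The second fault bears directly on the decision to take a dose forward, because each comparison is judged against a fixed level of 0.15.

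**Working it through.** **The plan's own figure.** Section 7.1 states: "A sample size of 25 per arm provides 90% power to detect a doubling (100% increase) in geometric mean influenza antibody titer A/H1N1", one-sided alpha 0.15, coefficient of variation 2.0. On the log scale SD = √ln(1 + 2.0²) = 1.269; SE = 1.269 × √(2/25) = 0.359; ln 2 / 0.359 = 1.932; power = Φ(1.932 − 1.036) = 81.5%. For A/H3N2 and B (ratio 1.8, coefficient 1.4) it is 83.1%. The 90% is not reproduced, but that is a separate matter. What carries over is that 7.1 looks to baseline adjustment for extra power.

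**Assumptions (not in the documents).** Baseline log SD 1.2; early titers with slope 1 and residual SD 0.3; Months 1 to 12 with a constant slope of 0.3, 0.5 or 0.7 and residual SD 1.0; no titer change within 24 hours; complete data; 25 per arm; arm-by-visit means, which a week-4 contrast needs.

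**Formulas.** With balanced data and a random intercept, the common slope is the plain average of the visit slopes: b = (4 × 1 + 4 × b₄)/8. Residual variance is 0.3² + (1 − b)² × 1.2² at early visits and 1.0² + (b − b₄)² × 1.2² at later ones. The model's SE uses the average of the two, times 2/25 and square-rooted; the true SD of the contrast uses the later one. Type I error ≈ 1 − Φ(1.036 × SE/SD).

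| Week-4 slope | b | Early variance | Later variance | Increase at week 4 | Average | Model SE | True SD | Type I error |
|---|---|---|---|---|---|---|---|---|
| 0.3 | 0.65 | 0.266 | 1.176 | 17.6% | 0.721 | 0.240 | 0.307 | 0.21 |
| 0.5 | 0.75 | 0.180 | 1.090 | 9.0% | 0.635 | 0.225 | 0.295 | 0.21 |
| 0.7 | 0.85 | 0.122 | 1.032 | 3.2% | 0.577 | 0.215 | 0.287 | 0.22 |

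Simulation of this set-up gives type I error of about 0.21-0.23, and variance increases down to about 2% at slope 0.7.

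**Second set of assumptions.** Log SD 1.269 at every visit, early-to-baseline correlation 0.9, later-visit correlation 0.8, week-4 correlation 0.3, 0.5 or 0.7. Simulated common slope 0.60, 0.70, 0.80; model SE 0.287, 0.256, 0.216 against a true SD of about 0.36, 0.32, 0.26; type I error 0.20, 0.21, 0.18.

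**Power from the slope alone, with the test held at 0.15.** With equal SDs, the week-4 variance relative to no adjustment is 1 − 2bρ + b², against 1 − ρ² with a week-4 slope. At ρ = 0.3 and b = 0.65 this is 1.0325 against 0.91 (+13.5%), and A/H1N1 power is 80.6% against 83.9%. At ρ = 0.5 it is 86.6% against 88.4%; at ρ = 0.7, 94.6% against 95.2%. Over ρ from 0.2 to 0.8 and early slope 0.9 to 1.0, variance rises 0.7% to 16.7% and power falls by 0 to 4 points.

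**Remedies.**
- Baseline-by-visit terms with the early draws kept and one variance: residual variances are 0.09 and 1.0, average 0.545, so type I error = 1 − Φ(1.036 × √0.545) = 0.22. The second set gives 0.21, 0.22, 0.18. The error rate is not repaired.
- Outcomes restricted to Months 1, 2, 6 and 12: the averaged variance equals the week-4 variance, and simulated type I error is about 0.14-0.16.
- A week-4-specific slope and variance: 0.14-0.15.

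**Scale.** Three doses and three titers make nine tests. If no dose works, 9 × 0.15 = 1.35 false positives are expected as planned, and 9 × 0.18 = 1.62 to 9 × 0.23 = 2.07 under the fault.

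**The case against.** The best defence is that the documents point to Table S-1. The opening of section 6 says that procedures and their timing are set out there, and 6.11 ties laboratory collection times to the schedule of events. The closing words of the 6.2 list also attach hourly draws to PBMCs, for which Table S-1 gives no such times, so they may have been meant only for the pharmacodynamic samples. This largely stands: a reader might infer that early titers certainly enter the primary model, and the documents do not support that. But 7.2, the section that defines the analysis, itself refers to several first-week titers, and no text says which source prevails.

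Next, 7.2 does not exclude baseline-by-visit terms. That is true; the single slope is inferred from silence. Those terms alone would not correct the standard error, however.

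The Td study in 1.4.2.4 reports that "A negative correlation was observed between baseline antibody titer and the change in antibody titer over 6 weeks". It is tempting to read this as showing how far below 1 the week-4 slope lies. It concerns tetanus and diphtheria antibodies in men aged 18 to 40, so it supports the direction only.

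Two more inferences go too far. The week-4 contrast is not biased, because randomization balances baseline whatever slope is used. Nor is the adjustment generally worse than none: with early slope 1 that requires ρ below 1/3.

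**Conclusion.** The primary model's outcome visits are not settled: 7.2, 6.2 and 6.3 conflict with Table S-1. If the early titers are analysed under the model as written, the main harm is a week-4 standard error that is too small, with type I error of about 0.18-0.23 instead of 0.15. The lesser harm is a week-4 variance about 2-18% higher, or at most about 4 points of power. If Table S-1 governs, early draws cause neither. The sizes depend on assumed SDs, slopes, correlations and early-titer reliability, none of which the documents give; the direction needs only that titers within 24 hours track baseline more closely, and with less scatter, than titers at 4 weeks.

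**What to change.** 1. Reconcile the titer times in 6.2, 6.3 and 7.2 with Table S-1.
2. State in 7.2 that the outcome visits are Months 1, 2, 6 and 12, with the pre-dose Day 0 titer as baseline. Neither 6.1 nor Table S-1 lists an influenza titer at screening, so the reference to a screening titer can go.
3. Name arm-by-visit and baseline-by-visit terms in the model.
4. If any titer within 24 hours is kept as an outcome, specify both baseline-by-visit terms and visit-specific (unstructured) variances. Either one alone leaves one of the two faults.

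The cost is wording only. If the early titers would otherwise have been assayed, the change also avoids up to 4 × 3 × 100 = 1,200 HAI results; if Table S-1 already governs, there is no such saving.

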Overall, this study demonstrated a stimulatory effect of entolimod on vaccination efficiency in a mouse model of age-related immunosenescence. This effect did not depend on the site of entolimod administration (indicating that it acts via a systemic mechanism) or on entolimod being part of the vaccine formulation. In addition, in “middle-aged” male mice, entolimod had a long-lasting positive effect on general health status that correlated with its immunomodulatory activity. Further studies are needed to clarify the mechanisms underlying the age- and gender-dependence of these effects. It should be noted that these effects were observed with doses of entolimod that are lower than its optimal efficacious dose in acute radiation syndrome.

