5.3 Method for Assigning Subjects to Treatment Groups

Study subjects will be randomized in a dose-escalated 4-arm study of entolimod in 3 possible doses or placebo (see table 2 below). Beginning in period 1, the first eight patients in the 1ug arm will be evaluated for safety and tolerability by the DSMB prior to the enrollment of the remainder of the 1ug arm. In addition, after review we will proceed with recruitment in period 2 of the 3ug arm. Again, safety and tolerability will be assessed in the first 8 patients of the 3ug arm during period 2. Similarly, after evaluation by the DSMB we will proceed with the remainder of the 3ug arm. In period 3 we will evaluate safety and tolerability in the first 8 subjects of the 10ug arm. An evaluation by the DSMB will be completed and we will proceed with the remainder of the 10ug arm until all subjects have been accrued. We will recruit the balance of the subjects remaining to be enrolled (to obtain 25 subjects per arm) pending safety review by the DSMB.

Randomization will be performed using Medidata Balance software, integrated into the electronic case report forms Medidata RAVE. A permuted block design will be used, with stratification by sex. Subjects and study center personnel involved in the care of subjects will be blinded to study drug assignment (entolimod vs. placebo).

Table 2. Dose-Escalated 4-arm Study

Arm	Placebo	1ug	3ug	10ug
Period 1	2	6		
Period 2	2		6	
Period 3	2			6

Dose Levels

Cohorts of subjects will be sequentially enrolled at progressively higher starting dose levels. The following dose levels are planned:

- Dose Level 1: 1 μ g
- Dose Level 2: 3 μ g
- Dose Level 3: 10 μ g

These doses are within the dose range of 1 μ g to 10 μ g and equal or greater than five times less than that which has been previously evaluated in healthy subjects and patients with advanced solid tumors.

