7.3 Subject Population(s) for Analysis

The primary analysis uses a modified intent-to-treat principle. Patients will be analyzed based on randomized arm using methods described previously. Exploratory analyses will assess whether a differential sex-based response to treatment exists for the primary outcomes and secondary outcomes of FI and QOL, using interaction terms in regression models.

8 Safety and Adverse Events

For safety analyses, AEs will be classified using the Medical Dictionary for Regulatory Activities (MedDRA). The severity of AEs will be graded by the investigator according to the Guidance for Industry Toxicity Grading Scale for Healthy Adult and Adolescent Volunteers Enrolled in Preventive Vaccine Clinical Trials. Concomitant medication use will be coded using the World Health Organization Drug Dictionary (WHODRUG) into Anatomical Therapeutic-Chemical classification (ATC) codes; these data descriptions will particularly focus on supportive medications and care provided in response to any study-study-induced adverse effects and to therapies for GVHD. For ECG assessment of QT intervals, correction by both the Bazett and Fridericia methods will be applied, and the data will be summarized by CTCAE grading categories in terms of absolute QTc and maximal QTc change from baseline.

A safety analysis will be conducted after 20 patients (5 per arm) have been randomized and completed the one-week safety follow-up period. After the last subject has completed their one-week safety follow-up period, there will be a temporary halt in additional participation pending analysis of safety outcomes, anticipated to be no longer than seven days. A safety report will be generated after the 20th patient completes 1 week follow up, summarizing all adverse events overall and by study arm while maintaining blind (groups denoted as A-D in random order). If appropriate, as described below, unblinded and subject-level adverse event data will be provided. Adverse events, both short term (14 days) and long term (through 365 days), will continue to be collected with ongoing monitoring as specified in the Data Safety Monitoring Plan (DSMP).

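### Randomisation is stratified by sex, but the primary titer model has no sex term; if sex predicts titer beyond baseline, the tests are slightly conservative

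*Combined protocol and SAP*

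**What the plan says.** Section 5.3 sets the allocation: "A permuted block design will be used, with stratification by sex". It names no other stratification factor and gives no block size.

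Section 7.2 (Primary Hypothesis) sets the model for each of the three log titers: "A hierarchical mixed-effects regression model will be fit separately for the 3 endpoints, adjusting for the baseline/screening observation of the titer". It adds: "The model will include random subject-specific intercepts and model time as discrete". The test is then defined: "The primary outcome comparison is a contrast analysis of the outcome at 4 weeks comparing each entolimod dose to placebo". On error rates the plan says: "we apply a one-sided test at alpha level 0.15 to each dose comparison (vs. placebo) and antibody titer combination, without multiplicity adjustment". Neither sex nor age is listed as a term.

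Sex appears in the analysis only in section 7.3: "Exploratory analyses will assess whether a differential sex-based response to treatment exists for the primary outcomes", using interaction terms. The same exploratory analysis covers the frailty index and quality of life. The secondary mixed models in section 7.2 name no covariates.

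Section 7.1 expects the analysis of covariance to gain power, and attributes that gain to the baseline titer alone.

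**The concern.** Stratifying by sex balances men and women across arms, so any difference in titer between the sexes largely cancels out of each dose-versus-placebo contrast. A model without sex still counts that difference as unexplained variation between subjects. The standard error it reports then describes a design in which sex was left to chance. Where sex is prognostic, the reported error exceeds the true one, the tests run below their nominal 0.15, and some power is lost.

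There is also a specification issue. Three doses and three titers give nine unadjusted one-sided tests. A plan that is silent on its only stratification factor leaves room to decide about adjustment after seeing the data. In addition, the interaction models of section 7.3 would normally carry a sex main effect, so they would differ from the primary model in more than the interaction.

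**Working it through.** **Inputs.** From section 7.1: 25 per arm, one-sided alpha 0.15, coefficient of variation (CV) 2.0 with a doubling for A/H1N1, and CV 1.4 with an 80% increase for A/H3N2 and B. From sections 5.3 and 7.2: sex is the stratum and is absent from the model. Assumed, because the documents give no figure: R², the share of week-4 residual log-titer variance that sex explains after baseline, at 0, 2%, 5% and 10%; a 50:50 sex split; and near-complete balance within sex.

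**Step 1: the plan's own figure.** For A/H1N1 the log SD is √ln(1 + 2.0²) = 1.269. The standard error of a contrast is 1.269 × √(2/25) = 0.359, and ln 2 / 0.359 = 1.93. With z = 1.036 at alpha 0.15, power is Φ(1.93 − 1.036) = 81.5% (81.2% with the t distribution). Section 7.1 states 90%. For A/H3N2 and B the log SD is √ln(1 + 1.4²) = 1.042, and power is 83.1% (82.8% with t), again against a stated 90%. That shortfall is a separate matter. It is noted here because the power comparisons below start from the recomputed base, not from 90%.

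**Step 2: standard error and size without sex.** The reported SE divided by the true SE is 1/√(1 − R²). The actual size is 1 − Φ(1.036/√(1 − R²)).

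**Step 3: power for A/H1N1.** Without sex it is Φ((1.93 − 1.036)/√(1 − R²)). With sex it is Φ(1.93/√(1 − R²) − 1.036).

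| Assumed R² | SE too wide by | Actual size | Power without sex | Power with sex |
|---|---|---|---|---|
| 0 | 0% | 0.150 | 81.5% | 81.5% |
| 2% | 1.0% | 0.148 | 81.7% | 82.0% |
| 5% | 2.6% | 0.144 | 82.1% | 82.8% |
| 10% | 5.4% | 0.137 | 82.7% | 84.1% |

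The largest loss is 84.1 − 82.7 = 1.4 points. For A/H3N2 and B at R² = 10% it is 85.7 − 84.4 = 1.3 points.

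**Step 4: what these R² values mean.** With a 50:50 split, the difference in log titer between the sexes is 2 × √R² × log SD. For A/H1N1 at R² = 10% this is 2 × 0.316 × 1.269 = 0.80, about a 2.2-fold difference in geometric mean titer. At 2% it is about 1.4-fold.

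**Step 5: simulation.** Four arms, 100 subjects, permuted blocks of 4 within sex (assumed), baseline correlation 0.5 (assumed), 6000 trials per setting. A single-visit analysis of covariance stood in for the week-4 contrast of the mixed model. At R² = 5%:

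- The mean reported SE divided by the empirical SD was 1.02–1.03 without sex and about 1.00 with it.
- The rejection rate with no dose effect was 0.142 without sex and 0.149 with it.
- Power to detect a doubling was 88.7% without sex and 89.2% with it.
- The mean estimate under a doubling was 0.694 with or without sex, against a true ln 2 = 0.693, so there is no sign of bias.

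**The case against.** The strongest case for leaving the plan alone is that the effect is conditional, small and on the safe side. If sex adds nothing to the baseline titer, the standard error is already right. The top of the assumed range needs roughly a twofold titer difference between men and women. The estimate is unbiased, the error is conservative, and this is a dose-screening trial that deliberately tests at one-sided 0.15 without multiplicity control. No dose choice plausibly turns on it. All of this stands, and it is why the point is low severity.

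The conservatism also depends on the balance achieved. Sections 3 and 5.3 describe staged opening of arms, periods of two placebo and six active subjects, accrual halts, and only four subjects in the first season. Incomplete blocks within sex would leave the balance imperfect and the conservatism smaller than tabulated. That stands too, although a sex term would then be useful for correcting the residual imbalance.

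A reader might infer from section 1.3.4 that the protocol itself shows sex to be prognostic for titer: "Further studies are needed to clarify the mechanisms underlying the age- and gender-dependence of these effects". It does not. The sentence concerns how entolimod's effect varied in mice, which is effect modification. The male-specific finding there is the frailty index, and the vaccine experiments are described in male mice only. Effect modification calls for the interaction analysis that section 7.3 already plans.

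A reader might also take the missing age term as part of the same mismatch. Age is not a stratification factor, so the argument about size does not apply to it. Section 1.1 contrasts the elderly with younger adults and gives no gradient above 65. Chance age imbalance is ordinary sampling error, which the standard error already covers.

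**Conclusion.** The mismatch is plain on the face of the documents: sex is the only randomisation stratum, and the stated primary model omits it. Its consequence is conditional. Only if sex predicts the week-4 log titer beyond baseline are the standard errors too wide. For an assumed R² of 2–10% with near-complete balance within sex, that means about 1–5% too wide, a size of 0.148–0.137 and at most about 1.4 points of power per contrast.

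The stronger statement, that the plan does report standard errors that are too wide, is not supported, because no section gives a prognostic effect of sex on titer. No bias and no inflated error rate follow in any case. The point is a free improvement of low severity, justified by matching the analysis to the randomisation and fixing the model in advance, not by a large numerical effect.

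**What to change.** In section 7.2, add sex, as the randomisation stratum, as a fixed effect in the three primary titer models. Do the same in the secondary linear mixed models for frailty, physical function and quality of life. Leave the sex-by-arm interaction in section 7.3 exploratory. Age at screening may be added as an optional precision covariate if the sponsor wishes; the choice should be fixed in advance and is not needed to match the design.

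The cost is one sentence and one degree of freedom out of about 95 in a single-visit analysis. Nothing new is collected, since sex must be known to randomise.
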